6.6 SAFETY ANALYSES

The safety and tolerability of rituximab will be evaluated from AEs, laboratory tests, vital signs, ECGs, chest X-rays, and as defined by protocol. Safety parameters will be summarized or listed for the safety population.

6.7 PHARMACOKINETIC ANALYSES

In the PK analysis population, non-linear mixed-effects modeling technique (NONMEM[®]) will be used to analyze the PK data with the population PK model developed from adult patients with GPA and MPA in the RAVE study ([Stone et al. 2010](#)). The primary PK parameters will be CL and volume of distribution. The secondary PK parameters (AUC_{0-inf} , C_{max}) will be calculated for each patient. PK concentrations will be summarized by visit. PK parameters will be tabulated and summarized (i.e., by mean, SD, coefficient of variation, median, and minimum and maximum). PK exposure and response relationships will be explored.

6.8

EXPLORATORY EFFICACY ENDPOINTS

[REDACTED]

6.9 EXPLORATORY PHARMACODYNAMIC ANALYSES

[REDACTED]

6.10 EXPLORATORY PATIENT-REPORTED OUTCOME ANALYSES

[REDACTED]

7. DATA COLLECTION AND MANAGEMENT

7.1 DATA QUALITY ASSURANCE

Roche will be responsible for data management of this study, including quality checking of the data. Data entered manually will be collected via EDC using eCRFs. Sites will be responsible for data entry into the EDC system. In the event of discrepant data, Roche will request data clarification from the sites, which the sites will resolve electronically in the EDC system.

Roche will produce an EDC Study Specification document that describes the quality checking to be performed on the data. Central laboratory data will be sent directly to

Roche, using Roche's standard procedures to handle and process the electronic transfer of these data.

eCRFs and correction documentation will be maintained in the EDC system's audit trail. System backups for data stored at Roche and records retention for study data will be consistent with Roche's standard procedures.

7.2 ELECTRONIC CASE REPORT FORMS

eCRFs are to be completed using a Sponsor-designated EDC system. Sites will receive training and have access to a manual for appropriate eCRF completion. eCRFs will be submitted electronically to Roche and should be handled in accordance with instructions from Roche.

All eCRFs should be completed by designated, trained site staff. eCRFs should be reviewed and electronically signed and dated by the investigator or a designee.

At the end of the study, the investigator will receive patient data for his or her site in a readable format on a compact disc that must be kept with the study records. Acknowledgement of receipt of the compact disc is required.

7.3 SOURCE DATA DOCUMENTATION

Study monitors will perform ongoing source data verification to confirm that critical protocol data (i.e., source data) entered into the eCRFs by authorized site personnel are accurate, complete, and verifiable from source documents.

Source documents (paper or electronic) are those in which patient data are recorded and documented for the first time. They include, but are not limited to, hospital records, clinical and office charts, laboratory notes, memoranda, patient-reported outcomes, evaluation checklists, pharmacy dispensing records, recorded data from automated instruments, copies of transcriptions that are certified after verification as being accurate and complete, microfiche, photographic negatives, microfilm or magnetic media, X-rays, patient files, and records kept at pharmacies, laboratories, and medico-technical departments involved in a clinical trial.

Before study initiation, the types of source documents that are to be generated will be clearly defined in the Trial Monitoring Plan. This includes any protocol data to be entered directly into the eCRFs (i.e., no prior written or electronic record of the data) and considered source data.

Source documents that are required to verify the validity and completeness of data entered onto the eCRFs must not be obliterated or destroyed and must be retained according to the policy for retention of records described in Section 7.5.

To facilitate source data verification, the investigators and institutions must provide the Sponsor direct access to applicable source documents and reports for study-related monitoring, Sponsor audits, and IRB or EC review. The investigational site must also allow inspection by applicable health authorities.

7.4 USE OF COMPUTERIZED SYSTEMS

When clinical observations are entered directly into an investigational site's computerized medical record system (i.e., in lieu of original hardcopy records), the electronic record can serve as the source document if the system has been validated in accordance with health authority requirements pertaining to computerized systems used in clinical research. An acceptable computerized data collection system allows preservation of the original entry of data. If original data are modified, the system should maintain a viewable audit trail that shows the original data as well as the reason for the change, name of the person making the change, and date of the change.

7.5 RETENTION OF RECORDS

Records and documents pertaining to the conduct of this study and the distribution of IMP, including eCRFs, electronic PRO data (if applicable), Informed Consent Forms, laboratory test results, and medication inventory records, must be retained by the Principal Investigator for at least 15 years after completion or discontinuation of the study, or for the length of time required by relevant national or local health authorities, whichever is longer. After that period of time, the documents may be destroyed, subject to local regulations.

No records may be disposed of without the written approval of Roche. Written notification should be provided to Roche prior to transferring any records to another party or moving them to another location.

8. ETHICAL CONSIDERATIONS

8.1 COMPLIANCE WITH LAWS AND REGULATIONS

This study will be conducted in full conformance with the ICH E6 guideline for Good Clinical Practice and the principles of the Declaration of Helsinki, or the laws and regulations of the country in which the research is conducted, whichever affords the greater protection to the individual. The study will comply with the requirements of the ICH E2A guideline (Clinical Safety Data Management: Definitions and Standards for Expedited Reporting). Studies conducted in the United States or under a US Investigational New Drug (IND) Application will comply with US FDA regulations and applicable local, state, and federal laws. Studies conducted in the European Union (EU)/EEA will comply with the EU Clinical Trial Directive (2001/20/EC).

8.2 INFORMED CONSENT

Roche's sample Informed Consent Form (and ancillary sample Informed Consent Forms such as a Child's Assent or Parent or Caregiver's Informed Consent Form, if applicable)

will be provided to each site. If applicable, it will be provided in a certified translation of the local language. Roche or its designee must review and approve any proposed deviations from Roche's sample Informed Consent Forms or any alternate consent forms proposed by the site (collectively, the "Consent Forms") before IRB/EC submission. The final IRB/EC-approved Consent Forms must be provided to Roche for health authority submission purposes according to local requirements.

The Consent Forms must be signed and dated by the patient or the patient's legally authorized representative before his or her participation in the study. The case history or clinical records for each patient shall document the informed consent process and that written informed consent was obtained prior to participation in the study.

The Consent Forms should be revised whenever there are changes to study procedures or when new information becomes available that may affect the willingness of the patient to participate. The final revised IRB/EC-approved Consent Forms must be provided to Roche for health authority submission purposes.

Patients must be re-consented to the most current version of the Consent Forms (or to a significant new information/findings addendum in accordance with applicable laws and IRB/EC policy) during their participation in the study. For any updated or revised Consent Forms, the case history or clinical records for each patient shall document the informed consent process and that written informed consent was obtained using the updated/revised Consent Forms for continued participation in the study.

A copy of each signed Consent Form must be provided to the patient or the patient's legally authorized representative. All signed and dated Consent Forms must remain in each patient's study file or in the site file and must be available for verification by study monitors at any time.

For sites in the United States, each Consent Form may also include patient authorization to allow use and disclosure of personal health information in compliance with the US Health Insurance Portability and Accountability Act (HIPAA) of 1996. If the site utilizes a separate Authorization Form for patient authorization for use and disclosure of personal health information under the HIPAA regulations, the review, approval, and other processes outlined above apply except that IRB review and approval may not be required per study site policies.

8.3 INSTITUTIONAL REVIEW BOARD OR ETHICS COMMITTEE

This protocol, the Informed Consent Forms, any information to be given to the patient, and relevant supporting information must be submitted to the IRB/EC by the Principal Investigator and reviewed and approved by the IRB/EC before the study is initiated. In addition, any patient recruitment materials must be approved by the IRB/EC.

The Principal Investigator is responsible for providing written summaries of the status of the study to the IRB/EC annually or more frequently in accordance with the requirements, policies, and procedures established by the IRB/EC. Investigators are also responsible for promptly informing the IRB/EC of any protocol amendments (see Section 9.5).

In addition to the requirements for reporting all AEs to the Sponsor, investigators must comply with requirements for reporting SAEs to the local health authority and IRB/EC. Investigators may receive written IND safety reports or other safety-related communications from Roche. Investigators are responsible for ensuring that such reports are reviewed and processed in accordance with health authority requirements and the policies and procedures established by their IRB/EC, and archived in the site's study file.

8.4 CONFIDENTIALITY

Roche maintains confidentiality standards by coding each patient enrolled in the study through assignment of a unique patient identification number. This means that patient names are not included in data sets that are transmitted to any Roche location.

Patient medical information obtained by this study is confidential and may only be disclosed to third parties as permitted by the Informed Consent Form (or separate authorization for use and disclosure of personal health information) signed by the patient, unless permitted or required by law.

Medical information may be given to a patient's personal physician or other appropriate medical personnel responsible for the patient's welfare, for treatment purposes.

Data generated by this study must be available for inspection upon request by representatives of the US FDA and other national and local health authorities, Roche monitors, representatives, and collaborators, and the IRB/EC for each study site, as appropriate.

8.5 FINANCIAL DISCLOSURE

Investigators will provide the Sponsor with sufficient, accurate financial information in accordance with local regulations to allow the Sponsor to submit complete and accurate financial certification or disclosure statements to the appropriate health authorities. Investigators are responsible for providing information on financial interests during the course of the study and for 1 year after completion of the study (i.e., last patient last visit).

9. STUDY DOCUMENTATION, MONITORING, AND ADMINISTRATION

9.1 STUDY DOCUMENTATION

The investigator must maintain adequate and accurate records to enable the conduct of the study to be fully documented, including, but not limited to, the protocol, protocol amendments, Informed Consent Forms, and documentation of IRB/EC and governmental approval. In addition, at the end of the study, the investigator will receive the patient data, which includes an audit trail containing a complete record of all changes to the data.

9.2 SITE INSPECTIONS

Site visits will be conducted by Roche or an authorized representative for inspection of study data, patients' medical records, and eCRFs. The investigator will permit national and local health authorities, Roche monitors, representatives, and collaborators, and the IRBs/ECs to inspect facilities and records relevant to this study.

9.3 ADMINISTRATIVE STRUCTURE

9.3.1 IxRS

An IxRS will be used to manage the dispensing of study drug (rituximab).

9.3.2 Central Laboratory

With the exception of ANCA (at screening only), C-reactive protein, erythrocyte sedimentation rate, urinalysis, and the urine dipstick pregnancy test (see Section 4.5.3.5), all laboratory tests will be analyzed by a central laboratory according to the Laboratory Manual.

9.4 PUBLICATION OF DATA AND PROTECTION OF TRADE SECRETS

The results of this study may be published or presented at scientific meetings. If this is foreseen, the investigator agrees to submit all manuscripts or abstracts to Roche prior to submission. This allows the Sponsor to protect proprietary information and to provide comments based on information from other studies that may not yet be available to the investigator.

Roche will comply with the requirements for publication of study results. In accordance with standard editorial and ethical practice, Roche will generally support publication of multicenter trials only in their entirety and not as individual center data. In this case, a coordinating investigator will be designated by mutual agreement.

Authorship will be determined by mutual agreement and in line with International Committee of Medical Journal Editors authorship requirements. Any formal publication of the study in which contribution of Roche personnel exceeded that of conventional

monitoring will be considered as a joint publication by the investigator and the appropriate Roche personnel.

Any inventions and resulting patents, improvements, and/or know-how originating from the use of data from this study will become and remain the exclusive and unburdened property of Roche, except where agreed otherwise.

9.5 PROTOCOL AMENDMENTS

Any protocol amendments will be prepared by the Sponsor. Protocol amendments will be submitted to the IRB/EC and to regulatory authorities in accordance with local regulatory requirements. Approval must be obtained from the IRB/EC and regulatory authorities (as locally required) before implementation of any changes, except for changes necessary to eliminate an immediate hazard to patients or changes that involve logistical or administrative aspects only (e.g., change in Medical Monitor or contact information).

10. INTERNAL MONITORING COMMITTEE

Because this is an open-label study, an Internal Monitoring Committee (IMC) composed of a Clinical Scientist, a Statistician, a Statistical Programmer Analyst, and a safety representative will review safety data from patients participating in this study. The IMC will be responsible for monitoring the overall safety of the patients in this study and will help to minimize patient exposure to unacceptable risk. From the time of its formation, the IMC will meet to review safety data as described in the IMC Charter.

Appendix 1 Schedule of Assessments

Visit ^a	Screen ^b	Week				Month								Follow-Up	WD	Extended Follow-Up ^e
		BL ^c	1	2	3	1	2	4	6	9	12	15	18	Every 3 Months after Month 18 ^d		
Day		1	8	15	22	29	60	120	180	270	365	455	545			
Medications																
Glucocorticoids IV ^f		x														
Glucocorticoids PO ^g		x	x	x	x	x	x	x	x	x	x	x	x	x	x	x
Pre-infusion medications ^h		x	x	x	x											
Rituximab IV infusion		x	x	x	x											
General Assessments																
Informed Consent/ Child's Assent	x															
Inclusion/exclusion criteria	x															
Medical history	x															
Pregnancy test (serum) ⁱ	x															
Pregnancy test (urine) ⁱ		x	x	x	x	x	x	x	x	x	x	x	x	x	x	x
12-Lead ECG ^j	x															
Height	x	x				x	x	x	x	x	x	x	x	x	x	x
Weight	x	x				x	x	x	x	x	x	x	x	x	x	x
Vital signs (pulse rate, systolic and diastolic blood pressure, and temperature)	x	x ^k	x ^k	x ^k	x ^k	x	x	x	x	x	x	x	x	x	x	x

Appendix 1 Schedule of Assessments (cont.)

Visit ^a	Screen ^b	Week				Month								Follow-Up	WD	Extended Follow-Up ^e	
		BL ^c	1	2	3	1	2	4	6	9	12	15	18	Every 3 Months after Month 18 ^d			
Day		1	8	15	22	29	60	120	180	270	365	455	545				
General Assessments (cont'd)																	
Physical examination	x	x	x	x	x	x	x	x	x	x	x	x	x	x	x	x	x
Chest X-ray ^l or CT scan ^m	x															x	
Safety Assessments																	
Adverse events		x	x	x	x	x	x	x	x	x	x	x	x	x	x	x	x
Concomitant medications	x ⁿ	x	x	x	x	x	x	x	x	x	x	x	x	x	x	x	x
Efficacy Assessments																	
Acute-Phase Reactant Assessments																	
C-reactive protein	x	x	x	x	x	x	x	x	x	x	x	x	x	x	x	x	x
Erythrocyte sedimentation rate	x	x	x	x	x	x	x	x	x	x	x	x	x	x	x	x	x

Appendix 1 Schedule of Assessments (cont.)

Visit ^a	Screen ^b	Week				Month								Follow-Up	WD	Extended Follow-Up ^e
		BL ^c	1	2	3	1	2	4	6	9	12	15	18	Every 3 Months after Month 18 ^d		
Day		1	8	15	22	29	60	120	180	270	365	455	545			
Laboratory Assessments																
Hematology (CBC)	x	x	x	x	x	x	x	x	x	x	x	x	x	x	x	x
Serum chemistry	x	x	x	x	x	x	x	x	x	x	x	x	x	x	x	x
Urinalysis with microscopy and albumin to creatinine ratio	x	x	x	x	x	x	x	x	x	x	x	x	x	x	x	x
HbA _{1c} ^s		x					x	x	x	x	x	x	x	x	x	x
HBsAg, HBcAb, and HCV Ab and HBV DNA ^t	x															
Tuberculosis screening	x															
Immunologic and Antibody Assessments																
Immunoglobulins	x	x				x	x	x	x	x	x	x	x	x	x	x
CD19 B cells		x ^q		x ^q				x	x	x	x	x	x	x	x	x
FACS panel		x	x	x	x	x	x	x	x	x	x	x	x	x	x	x
Serum HACA sample		x						x	x	x			x	x ^u	x	x ^u
Serum ANCA sample ^{v, w}	x					x			x		x		x	x ^u	x	x ^u
Pharmacokinetic Assessments																
Sample for rituximab levels		x ^x	x ^y	x ^y	x ^x	x	x	x	x	x			x	x ^u	x	x ^u

ANCA = anti-neutrophil cytoplasmic antibody; CBC = complete blood count; [REDACTED]; [REDACTED]; [REDACTED]; CT = computed tomography; ECG = electrocardiogram; eCRF = electronic Case Report Form; FACS = fluorescence-activated cell sorter; GFR = glomerular filtration rate; GPA = granulomatosis with polyangiitis; HbA_{1c} = glycosylated hemoglobin; HBcAb = hepatitis B core antibody; HBsAg = hepatitis B surface antigen; HBV = hepatitis B virus; HCV Ab = hepatitis C virus antibodies; IV = intravenous; LLN = lower limit of normal; MPA = microscopic polyangiitis; PK = pharmacokinetic; PO = by mouth; PVDI = Pediatric Vasculitis Damage Index; WD = withdrawal.

Appendix 1 Schedule of Assessments (cont.)

- ^a For visit windows, please refer to [Appendix 2](#).
- ^b The screening visit must be completed within 28 days of the baseline visit.
- ^c Assessments performed within 14 days of the baseline visit do not have to be repeated at the discretion of the investigator and if not clinically indicated.
- ^d Until the common closeout date.
- ^e At the common closeout date, patients whose *peripheral* B cells remain depleted, will continue to attend study visits every 3 months until their *peripheral* B-cell counts have returned to *pre-rituximab* baseline levels or to within the normal range for the population, whichever is lower.
- ^f Three times daily IV infusions of 30 mg/kg of methylprednisolone (up to 1 g/day, or equivalent) may be administered at any time, up to and including Day 1 (prior to the first rituximab infusion). If clinically indicated, and at the discretion of the investigator, an additional three daily doses of methylprednisolone (up to 1 g/day) can be given by IV infusion. No more than six doses in total can be given. All doses must be completed prior to the first rituximab infusion. The first rituximab infusion must occur no later than 14 days after the last dose of methylprednisolone infusion.
- ^g All patients will receive concomitant oral prednisolone or prednisone (1 mg/kg/day; up to 60 mg/day, or equivalent), which will be tapered to a minimum of 0.2 mg/kg/day (or 10 mg/day, whichever is lower) no later than Month 6.
- ^h Patients should be premedicated with paracetamol/acetaminophen and cetirizine hydrochloride (or similar antihistamine), both according to labeled age-related doses, to be given 1 hour (\pm 15 minutes) before each infusion of rituximab.
To be completed for female patients of childbearing potential.
- ⁱ After screening, only if clinically indicated.
- ^j Vital signs should be taken immediately prior to infusion. During an infusion, record vital signs every 15 minutes for 1 hour; then every 30 minutes; and then at least 1 hour after the completion of the infusion.
- ^k To be completed at screening and, if normal, only if indicated thereafter. If the chest X-ray is abnormal, repeat at Month 1 and as indicated thereafter.
- ^l CT scan to be completed only if indicated.
- ^m Within the last 365 days of the screening visit
- ⁿ [REDACTED]
- ^o [REDACTED]
- ^p CD19 B-cell samples to be obtained prior to infusion of rituximab
- ^q [REDACTED]
- ^r [REDACTED]
- ^s Fasting is not required.
- ^t After screening, only if clinically indicated.
- ^u After the Month 18 visit, samples should be taken every 6 months thereafter.
- ^v ANCA testing performed at the screening visit to support a diagnosis of GPA or MPA may be performed locally or centrally. All other ANCA testing to be performed centrally.
- ^w Also to be performed at time of flare.
- ^x PK samples to be obtained prior to infusion of rituximab and 30 minutes following infusion of rituximab.
- ^y PK samples to be obtained prior to infusion of rituximab.

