Prior to the first rituximab infusion, patients must receive three doses of methylprednisolone at 30 mg/kg/day (up to 1 g/day) by intravenous (IV) infusion that can occur any time, up to and including Day 1. If clinically indicated, and at the discretion of the investigator, additional daily doses (up to three) of methylprednisolone (30 mg/kg, up to 1 g/day) can be given by IV infusion. No more than six doses of methylprednisolone in total can be given. All methylprednisolone doses must be completed prior to the first rituximab infusion. The first rituximab infusion must occur no later than 14 days after the last dose of methylprednisolone infusion. Subject to the investigator's discretion, corticosteroid premedication with an IV infusion of 100 mg of methylprednisolone may be administered at least 30 minutes prior to the infusion of rituximab (but not prior to clinical assessments) if the patient has experienced an IRR with a previous rituximab infusion.

Rituximab will be administered to patients as four weekly IV infusions of 375 mg/m² on Days 1, 8, 15, and 22. The dose will be calculated using a patient's body surface area (BSA) at screening. Infusions can be given in a day care or inpatient setting. It is acceptable to hospitalize a patient as per local clinical practice. All patients will receive concomitant oral prednisolone or prednisone (maximum, 1 mg/kg/day or up to 60 mg/day, whichever is less), which will be tapered to a minimum of 0.2 mg/kg/day (or 10 mg/day, whichever is lowest) no later than by Month 6. Following completion of rituximab infusions on Day 22, patients will complete study visits at Months 1, 2, 4, and 6 and will undergo assessments in accordance with the schedule of assessments.

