Patients should be medicated pre-infusion with paracetamol/acetaminophen and cetirizine hydrochloride (or similar antihistamine), both according to labeled age-related doses, to be given 1 hour (\pm 15 minutes) before each infusion of rituximab. Subject to investigator's discretion, corticosteroid premedication with an IV infusion of 100 mg of methylprednisolone may be administered at least 30 minutes prior to infusion of rituximab (but not prior to clinical assessments) if the patient has experienced an IRR with a previous rituximab infusion.

Methylprednisolone

Prior to the first rituximab infusion, patients must receive three doses of methylprednisolone at 30 mg/kg/day (up to 1 g/day) by IV infusion that can occur any time after screening, up to and including Day 1. If clinically indicated, and at the discretion of the investigator, additional daily doses (up to three) of methylprednisolone (30 mg/kg, up to 1 g/day) can be given by IV infusion. No more than six doses of methylprednisolone in total can be given. All methylprednisolone doses must be completed prior to the first rituximab infusion. The first rituximab infusion must occur no later than 14 days after the last dose of methylprednisolone infusion.

Prednisolone or Prednisone

On Day 1 and following completion of IV glucocorticoids, all patients will receive concomitant oral prednisolone or prednisone (1 mg/kg/day or up to 60 mg/day or equivalent, whichever is lower), the dose of which will be tapered to a minimum of 0.2 mg/kg/day (or 10 mg/day, whichever is the lowest) no later than Month 6.

The general guidance on the suggested oral steroid dose-tapering schedule is to taper from 1 mg/kg/day (60 mg/day, maximum) at the start of treatment, to 0.8 mg/kg/day by Month 1, and then by 0.1–0.2 mg/kg/day each month to 0.2 mg/kg/day (or 10 mg/day, whichever is the lowest), which should be reached no later than Month 6.

Oral prednisone (used in some non-UK sites) may be substituted for prednisolone at the same dose as long as there is no hepatic impairment.

The steroid-tapering practice is specific to a particular patient and as such should be tailored individually for each patient at the time of study entry, at the discretion of the investigator.

Comparator

Not applicable.

Statistical Methods

Primary Analysis

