4.3.2.2 Methylprednisolone (Non-Investigational Medicinal Product)

4.3.2.2.1 Dosage, Administration, and Compliance

Patients must receive three daily doses of 30 mg/kg of methylprednisolone (up to 1 g/day) or the equivalent dose of other glucocorticoids by IV infusion, which can occur at any time, up to and including Day 1. If clinically indicated, and at the discretion of the investigator, additional doses (up to three) of methylprednisolone (30 mg/kg, up to 1 g/day, or equivalent) can be given by IV infusion. No more than six doses of methylprednisolone in total may be given. All methylprednisolone doses must be completed prior to the first rituximab infusion.

The first rituximab infusion must occur no longer than 14 days after the final IV glucocorticoid dose; the final IV glucocorticoid dose may be given on Day 1 (prior to the first rituximab infusion).

Compliance will be assessed according to completion of a glucocorticoid log.

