- f Three times daily IV infusions of 30 mg/kg of methylprednisolone (up to 1 g/day, or equivalent) may be administered at any time, up to and including Day 1 (prior to the first rituximab infusion). If clinically indicated, and at the discretion of the investigator, an additional three daily doses of methylprednisolone (up to 1 g/day) can be given by IV infusion. No more than six doses in total can be given. All doses must be completed prior to the first rituximab infusion. The first rituximab infusion must occur no later than 14 days after the last dose of methylprednisolone infusion.
- g All patients will receive concomitant oral prednisolone or prednisone (1 mg/kg/day; up to 60 mg/day, or equivalent), which will be tapered to a minimum of 0.2 mg/kg/day (or 10 mg/day, whichever is lower) no later than Month 6.
- h Patients should be premedicated with paracetamol/acetaminophen and cetirizine hydrochloride (or similar antihistamine), both according to labeled age-related doses, to be given 1 hour (\pm 15 minutes) before each infusion of rituximab.
- i To be completed for female patients of childbearing potential.
- j After screening, only if clinically indicated.
- k Vital signs should be taken immediately prior to infusion. During an infusion, record vital signs every 15 minutes for 1 hour; then every 30 minutes; and then at least 1 hour after the completion of the infusion.
- l To be completed at screening and, if normal, only if indicated thereafter. If the chest X-ray is abnormal, repeat at Month 1 and as indicated thereafter.
- m CT scan to be completed only if indicated.
- n Within the last 365 days of the screening visit.
- o [REDACTED]
- p [REDACTED]
- q CD19 B-cell samples to be obtained prior to infusion of rituximab.
- r [REDACTED]
- s Fasting is not required.
- t After screening, only if clinically indicated.
- u After the Month 18 visit, samples should be taken every 6 months thereafter.
- v ANCA testing performed at the screening visit to support a diagnosis of GPA or MPA may be performed locally or centrally. All other ANCA testing to be performed centrally.
- w Also to be performed at time of flare.
- x PK samples to be obtained prior to infusion of rituximab and 30 minutes following infusion of rituximab.
- y PK samples to be obtained prior to infusion of rituximab.

[REDACTED]

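### Schedule footnote f can be read as methylprednisolone three times a day; the five passages that state the regimen and the Appendix 2 spacing rule give it once daily

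*Protocol*

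**What the plan says.** The IV glucocorticoid row in protocol Appendix 1 carries footnote f, which opens "Three times daily IV infusions of 30 mg/kg of methylprednisolone (up to 1 g/day, or equivalent) may be administered at any time". It continues with "an additional three daily doses of methylprednisolone (up to 1 g/day) can be given by IV infusion" and "No more than six doses in total can be given". SAP Appendix 2 reproduces the schedule, and its footnote f opens with the same words: "Three times daily IV infusions of 30 mg/kg of methylprednisolone".

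Five protocol passages state the regimen:

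- Synopsis, Remission Induction Phase: "patients must receive three doses of methylprednisolone at 30 mg/kg/day (up to 1 g/day) by intravenous (IV) infusion".
- Synopsis, Methylprednisolone paragraph: "patients must receive three doses of methylprednisolone at 30 mg/kg/day (up to 1 g/day) by IV infusion".
- Section 3.1.2: the same wording as that Synopsis paragraph.
- Section 4.3.2.2.1, the dosing section for this drug: "Patients must receive three daily doses of 30 mg/kg of methylprednisolone (up to 1 g/day" (the parenthesis closes after the cap).
- Section 4.5.6.2: again three doses at 30 mg/kg/day with the 1 g/day limit.

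Protocol Appendix 2 (visit windows) places the second and third infusions, and each optional extra one, at least a day after the one before. Footnote a of the schedule points there: "For visit windows, please refer to" Appendix 2.

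**The concern.** A schedule of assessments is often the page that site staff work from. Here it carries a frequency for high-dose IV steroid, in children from 2 years of age, that can be read differently from the dosing section. As the table was extracted, the IV glucocorticoid row is marked only at Day 1, so a reader sees one marked day beside a footnote that opens with a three-times-daily phrase. In fairness, the same footnote allows the infusions at any time up to and including Day 1.

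What is at stake is the dosing instruction, not the analysis. The records would describe what happened without saying which text a site should have followed. SAP output EX006SP groups the number of methylprednisolone doses as 1, 2, 3 or more than 3, so three infusions on one day and three on successive days both count as 3. Only its treatment-duration row, or the start and end days in listing EX004SP, would separate the two.

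**Working it through.** The plan gives no derived figure to reproduce. The check compares the texts and then works out how far apart the two readings are.

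**Frequency and spacing**

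| Source | Number of doses | Frequency or spacing |
|---|---|---|
| Footnote f, opening words | not stated separately from frequency | can be read as three per day |
| Footnote f, later sentences | three extra, at most six in all | extra doses described as daily |
| Synopsis (two passages), 3.1.2, 4.5.6.2 | three | 30 mg/kg/day |
| 4.3.2.2.1 | three | daily |
| Protocol Appendix 2 | three, plus up to three extra | at least 1 day between doses |

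Six in all less three extra leaves three base doses (6 − 3 = 3), which matches the count elsewhere. The disagreement is therefore about how many infusions fall on one day. Three infusions on one day break the one-day gap whatever the child weighs.

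Section 5.2.3.1 also mentions the pre-treatment, but gives only a minimum number of doses, with no rate and no interval. It supports neither reading.

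**Single-day amount**

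Inputs: 30 mg/kg per infusion and a limit of 1000 mg/day (footnote f and the dosing sections). Body weight w in kg is an assumption, because the documents give no weight distribution.

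- Dosing sections: min(30w, 1000) mg.
- Footnote read literally, before the cap: 3 × 30w = 90w mg.
- The cap is reached at 1000/90 = 11.1 kg under the literal reading, and at 1000/30 = 33.3 kg under the dosing sections.

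| w (kg) | Dosing sections (mg) | Literal, uncapped (mg) | Literal, capped (mg) | Capped ratio |
|---|---|---|---|---|
| 10 | 300 | 900 | 900 | 3.0 |
| 20 | 600 | 1800 | 1000 | 1.67 (hypothetical) |
| 30 | 900 | 2700 | 1000 | 1.11 (hypothetical) |
| 40 | 1000 | 3600 | 1000 | 1.0 |

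Up to 11.1 kg, three full infusions fit under the footnote's own cap and the ratio is 90w/30w = 3. Above that, three infusions of 30 mg/kg and the 1 g/day limit cannot both be met. At 20 kg, for example, capping at 1000 mg makes each infusion average 1000/(3 × 20) = 16.7 mg/kg rather than 30. The rows between 11.1 and 33.3 kg therefore describe a truncated regimen that no passage states. From 33.3 kg the capped daily amounts coincide.

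The footnote states no number of days, so no course total is computed.

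**The case against.** The strongest reply is that footnote f largely answers itself. Its opening can be parsed as daily infusions given on three occasions. That parse fits the 1 g/day limit, the extra doses described as daily and the six-dose total. Footnote a leads to the spacing rule, and five passages agree, one of them the section that exists to define this drug's dosage. The amendment's summary of changes says the Synopsis text was updated to agree with Sections 4.3.2.2.1 and 4.5.6.2, which suggests the sponsor already treats those sections as the reference. The SAP copy sits in an analysis document, and the footnote to output DS201SP gives the common closeout date as 10 May 2018, 18 months after the last enrolment. Correcting the SAP would therefore alter nobody's dosing.

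Most of this stands. It makes a wording slip the likely explanation and keeps the point small. It does not remove the conflict. The opening words can still be read as three per day, they are current text in both documents, and the reader must go to another appendix to find the spacing rule that excludes that reading.

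A reader might infer that the protocol prescribes 90 mg/kg/day, or that smaller children were given up to three times the intended amount. The documents support neither: the first ignores the rest of the footnote, and nothing shows how any site dosed. A reader might also take the ratios between 1 and 3 as the size of the discrepancy across the weight range. They are hypothetical, for the reason shown in the working.

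**Conclusion.** The point holds as a wording conflict in operative dosing text. Footnote f can be read as three infusions a day, against five passages that give a daily rate and an appendix that requires at least a day between doses.

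Read literally, the single-day amount is three times that stated elsewhere. This is compatible with the footnote's own cap only up to about 11.1 kg. With the cap applied, the daily amounts are equal from about 33.3 kg. The spacing conflict applies at all weights. How many enrolled children fall below either weight is unknown. The protocol does contemplate very small patients, since Section 4.5.3.5 makes arrangements for blood draws in those under 13 kg.

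It would be tempting to conclude that the steroid ambiguity distorts the safety, PK or remission results. Nothing in the documents shows that, and it is not claimed. The point deserves correction because it concerns high-dose steroid in young children and costs almost nothing to settle.

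**What to change.** Reconcile footnote f in protocol Appendix 1 with the Synopsis, Sections 3.1.2, 4.3.2.2.1 and 4.5.6.2, and protocol Appendix 2, so that frequency, amount per dose, daily cap and spacing agree in every place. Make the same change in SAP Appendix 2, for consistency between the documents. Which text stands is for the clinical team to decide.

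The cost is a rewording of one protocol footnote and its SAP copy. Sample size, data collection and the planned outputs are unaffected. Listing EX004SP, as already specified, can be used to check whether any patient had more than one methylprednisolone infusion on the same day before the first rituximab infusion.
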